6.2 Use of Investigational Products

Subjects will not be requested or forced to smoke CC or to use THS 2.2 and will be free to stop using their allocated product (THS 2.2 or CC) at any time during the study. THS 2.2 will not be promoted for commercial distribution or test market.

Confidentiality Statement

Data and information contained in this document are considered to constitute trade secrets and confidential commercial information, and the legal protections provided to such trade secrets and confidential information are hereby claimed under the provisions of applicable law. No part of this document may be publicly disclosed without the written consent of Philip Morris Products S.A.

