### 7.2.8 Cough Questionnaire

Subjects will self-report the respiratory symptom ‘cough’ using a visual analog scale (VAS), three Likert scale questions, and one open ended question at V3, V7, V10, and V16.

Subjects will be asked if they have experienced a regular need to cough, (*i.e.*, whether they have coughed several times in the previous 24 hours prior to assessment). If the answer is ‘yes’, subjects will be asked to complete the questionnaire.

The VAS will assess how bothersome cough is to the subject ranging from ‘not bothering me at all’ to ‘extremely bothersome’, and this will be given a numeric value between 0 and 100, measured on a 100 mm scale.

Subjects will also be asked to assess the intensity and frequency of cough and the amount of sputum production on Likert scales as presented in Table 11.

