### 10.2 Full Analysis Set - As Exposed (FAS-EX)

The FAS-EX consists of all subjects in FAS-AR who have at least one record of reported product use diary post randomization.

The exposure assignment for the FAS-EX will be actual product exposure as explained in Section 4.1.2 “Definition of Product Use Pattern Categories”. In particular, the analysis on FAS-EX will be conducted using time-varying product use categories, where Month 1 – Month 6 will be analyzed using product use categories defined for ]V4, V10[, and Month 7 – Month 12 data will be analyzed using the product use categories defined for ]V4, V16[.

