The MMRM analysis approach adopted in Section 12.7.1.2 “Smokers’ Health Profile Endpoints Evaluation” will be used to compare between THS-use and CC-use at V7, V10, and V16, using a 5% Type I error with no adjustment for multiplicity. Lung function data, apart from RV and FEV1 %pred (post-bronchodilator), will be analyzed in the original scale (Tables 15.2.4.6.1-15.2.4.6.3 and 15.2.4.8.1-15.2.4.8.3), and cardiovascular data will be analyzed in original scale for Apo A1, Apo B, Apo B/Apo A1, LDL-C, HbA1c, blood pressure, weight, and waist circumference, and in logarithmic scale for albumin in urine (expressed as concentration adjusted to creatinine), MPO, hs-CRP, fibrinogen, homocysteine, and platelet count.

The models will only include terms for visit, sex, Caucasian origin, age, smoking intensity, baseline level, product use pattern category, and the interactions of visit with both baseline level and product use category. Site will be included as a random effect. The ratios/differences will also be compared for THS-use versus CC-use and Dual-use versus CC-use, using a 5% Type I error. The estimates of the difference or ratio/percent reduction will be presented together with 95% CI. These estimates will be produced for THS 2.2 versus CC arms for the FAS-AR and PP populations.

All summaries and analyses will be performed on the FAS-EX, FAS-AR, and PP populations.

In addition, a sensitivity analysis will be produced for the albumin in urine creatinine-adjusted endpoint and the Apo B/Apo A1 endpoint in which the derived values will be calculated using half LLOQ values for the denominator in cases where the value is below LLOQ. This sensitivity analysis will be performed for the FAS-EX population to compare THS-use versus CC-use and Dual-use vs CC-use (Table 15.2.4.8.1.1).

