### 12.7.2.5 Cough Symptoms

Cough symptoms will be assessed by means of the cough questionnaire, as described in Section 7.2.8 “Cough Questionnaire”.

Descriptive analysis for change from Baseline will be presented for the VAS score and evaluating the level of cough bother at V7, V10, and V16. For the calculation of the change from Baseline, missing VAS values will be imputed with zero when no cough was reported.

The responses to the individual items, including the VAS score, change from Baseline, 3 Likert scales measuring the intensity and frequency of cough, and the amount of sputum production will be listed and summarized using the number of subjects who reported to experience cough as denominator (Listings 15.3.3.5; Tables 15.2.4.9.1 and 15.2.4.9.2).

The number and percentage of subjects reporting a cough will be summarized by randomization arm and product use pattern categories.

The answers to the open question related to any other important observation will be listed.

In addition, a logistic mixed-effects regression model for repeated measures will be used to compare the percentages of subjects reporting the need to cough between THS-use and CC-use at V7, V10, and V16 (Table 15.2.4.10). The model will include terms for visit, sex, Caucasian origin, age, smoking intensity, baseline cough, product use pattern category, and the interactions of visit with both baseline cough and product use category. Site will be included as a random effect. The point and 95% CI of LS means of the proportion of subjects reporting need to cough and their odds ratio will be presented for THS-use versus CC-use and also for Dual-use versus CC-use.

The SAS code for the logistic regression model to be used is shown below:

```
Proc glimmix data=_data_ method=rspl maxopt=200;
Class subject baseline product_use site sex caucasian_origin
visit;
Model endpoint = baseline sex caucasian_origin age
smoking_intensity product_use visit baseline*visit
product_use*visit / dist=binary link=logit ddfm=kr;
```

```
Random site;  
Random visit / subject=subject type=un residual;  
Lsmeans product_use*visit / slice=visit alpha=0.05 diff cl  
pdiff ilink or;  
Run;
```

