In case of model convergence issues, this will be reported in the study report and additional covariance structures will be investigated with the following order: heterogeneous compound symmetry (type=csh), heterogeneous toeplitz (type=toeph), heterogeneous autoregressive (1) (type=arh(1)), and variance components (type=vc). All descriptive summaries will be performed on the FAS-EX and PP populations and the logistic regression will be performed on the FAS-EX.

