## 16.2 Statistical Considerations for the Definition of Analysis

### Populations

In pivotal parallel group pharmaceutical therapy superiority studies the general approach is to analyze the intention-to-treat (ITT) population. In such studies the product efficacy and the product compliance are generally highly correlated as the product effects may be detectable by the subject (*e.g.*, relief from symptoms). The drivers for product use (ultimately product compliance) for tobacco products are not the same as in a pharmaceutical setting. Smokers decide to smoke, despite the known risks and adverse health effects, based on social, cultural, personal, and psychological factors. In addition, classical ITT analyses would compare subjects based on their assigned (intended) exposure, in order to preserve randomization, without regard to the subsequent compliance. As a result, estimates of exposure effects from these comparisons would be confounded with compliance, and can be seriously underestimated when noncompliance is high [26]. Therefore the ITT approach may not be optimal in randomized studies evaluating modified risk tobacco products, as these products are targeting risk reduction which may not be the main factor influencing the choice of tobacco products used by the subjects and the level of noncompliance to the product (*e.g.*, Dual-use) may not be negligible.

The aim of this study is to demonstrate the real-world effect that could be achieved by the exposure to THS 2.2, in terms of favorable changes in the ‘smokers ‘health profile’ endpoints. In this perspective, the following considerations were taken into account in order to measure effect in this study:

- The primary analysis is designed to assess the effect in all subjects as per actual use of study products.
- The subjects are allowed to use the THS 2.2 product in a truly ad libitum setting (no product use restrictions are made in the study protocol).

To support the interpretation of the results, the analysis of the primary objective is conducted on the PP population and on the FAS-AR (see Section 12.7.1.3), and including a sensitivity analysis conducted in the context of the exploratory exposure-response model (see Section 12.7.3.2).

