Table 15.2.4.8.3	Analysis of Additional Cardiovascular Disease Markers – FAS-AR			
Table 15.2.4.9.1	Summary of Cough Assessment Over Study – FAS-EX			
Table 15.2.4.9.2	Summary of Cough Assessment Over Study – PP Population			
Table 15.2.4.10	Analysis of Proportion of Subjects Reporting Need to Cough Over Study – FAS-EX			
Table 15.2.4.11.1	Descriptive Statistics of MCEQ Subscales – FAS-EX			
Table 15.2.4.11.2	Descriptive Statistics of MCEQ Subscales – PP Population			

Table No.	Title	Topline (Y/N)	Safety (Y/N)	Clinical Trial.gov (Y/N)
Table 15.2.4.12.1	Analysis of MCEQ Subscales – FAS-EX			
Table 15.2.4.12.2	Analysis of MCEQ Subscales – PP Population			
Table 15.2.4.13.1	Descriptive Statistics of FTND Results – FAS-EX			
Table 15.2.4.13.2	Descriptive Statistics of FTND Results – PP Population			
Table 15.2.4.14.1	Descriptive Statistics of Intent to Use THS 2.2 Questionnaire – FAS-EX			
Table 15.2.4.14.2	Descriptive Statistics of Intention to Use THS 2.2 Questionnaire – PP Population			
Table 15.2.4.15	Descriptive Statistics of Distribution of Dual Use over Randomized Exposure Period – FAS-EX			
Table 15.2.4.16	Analysis of Final Propensity Model – FAS-AR			
Table 15.2.4.17	Analysis of Exposure-Response Relationship of Dual Use – FAS-AR			
Table 15.2.5.1	Summary of Product Use Pattern – FAS-EX	Y		

Table No.	Title	Topline (Y/N)	Safety (Y/N)	Clinical Trial.gov (Y/N)
Table 15.2.5.1.1	Summary of Product Use Pattern by Sex - FAS-EX			
Table 15.2.5.1.2	Summary of Product Use Pattern by Consumption Level - FAS-EX			
Table 15.2.5.2	Summary of Product Use Pattern - Safety Population			
Table 15.2.5.3	Summary of Product Use Pattern - FAS-AR	Y		
Table 15.2.5.4	Summary of Detailed Product Use Pattern - FAS-EX			
Table 15.2.6.1	Summary of Adverse Events – Safety Population		Y	
Table 15.2.6.2	Summary of Adverse Events by Product Use Pattern Category – Safety Population	Y	Y	
Table 15.2.6.3	Summary of Adverse Events by System Organ Class and Preferred Term – Safety Population		Y	
Table 15.2.6.3.1	Summary of Monthly Adverse Events by System Organ Class and Preferred Term – Safety Population		Y	
Table 15.2.6.4	Summary of Adverse Events by Product Use Pattern Category, System Organ Class and Preferred Term – Safety Population	Y	Y	

Table No.	Title	Topline (Y/N)	Safety (Y/N)	Clinical Trial.gov (Y/N)

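### Need to cough, a symptom subjects can act on, is modelled only by actual product use; add the same model by randomised arm

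*SAP*

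**What the plan says.** SAP 12.7.2.5 plans a repeated-measures logistic model to "compare the percentages of subjects reporting the need to cough between THS-use and CC-use at V7, V10, and V16", and the same for Dual-use versus CC-use. The model adjusts for baseline cough, among other terms. On populations it says: "All descriptive summaries will be performed on the FAS-EX and PP populations and the logistic regression will be performed on the FAS-EX". The output list in SAP 16.4 has one model table for cough, 15.2.4.10, titled "Analysis of Proportion of Subjects Reporting Need to Cough Over Study – FAS-EX".

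The outcome is a yes/no self-report. SAP 7.2.8: "Subjects will be asked if they have experienced a regular need to cough", referring to the previous 24 hours. Protocol 6.2 leaves subjects "free to stop using their allocated product (THS 2.2 or CC) at any time during the study".

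For the lung function and cardiovascular markers under the same secondary objective, SAP 12.7.2.4.1 says: "All summaries and analyses will be performed on the FAS-EX, FAS-AR, and PP populations".

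Two other places plan cough output. SAP 12.7.2.5 also promises counts of subjects reporting a cough by randomisation arm and by use category. SAP 12.7.4.4.6 repeats the cough summaries on the Safety population, with the counts by use category.

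**The concern.** Grouping by actual use is a grouping formed after randomisation. SAP 16.2 defends it by contrast with drug trials, where "the product efficacy and the product compliance are generally highly correlated as the product effects may be detectable by the subject". It argues that the drivers of tobacco use are different. That argument is weakest for an outcome the subject feels. A THS-arm subject who coughs may return to cigarettes and drop out of THS-use, and one whose cough settles may stay. The symptom can then shape the groups that are compared on it.

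At stake is the reading of one odds ratio and its interval. A value below 1 could reflect less coughing on THS, or coughers leaving THS-use, and no modelled estimate by randomised arm would help to separate the two.

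**Working it through.** **No plan figure to reproduce.** The documents give no sample size, expected rate or precision for cough. Prevalence and retention by cough status below are assumptions.

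**1. Can use after a cough report set the group?** SAP 10.2 says "the analysis on FAS-EX will be conducted using time-varying product use categories": the six-month category applies to V7 and V10, the twelve-month category to V16.

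- V7. Under SAP 16.3.2, each day in the first three months has weight 1, and days in the second three months have weights rising from 1. With the nominal days in SAP Table 17 (V7 = day 92, V10 = day 183), the first part is days 2 to 92, total weight 91. The second is days 93 to 182, with weights 1 to 90, total 90 × 91/2 = 4,095. The share after V7 is 4,095/(4,095 + 91) = 98%. A subject in THS-use up to V7 who is then in CC-use becomes a Switcher and leaves the contrast, V7 cough report included.
- V16. In SAP Table 20, THS-use followed by CC-use gives Switcher, and THS-use followed by Dual-use gives Dual-use. Either way, a change after V10 removes the subject from THS-use at V16.

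Baseline cough precedes all of this, so adjusting for it cannot undo selection on later cough.

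**2. Closed form, no THS effect, selection on cough at the same visit.** Let p be cough prevalence in both arms, s1 and s0 the proportions of THS-arm coughers and non-coughers who stay in THS-use, and r1 and r0 the same for the CC arm and CC-use.

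- Odds of cough in THS-use = p·s1 / [(1 − p)·s0].
- Odds of cough in CC-use = p·r1 / [(1 − p)·r0].
- Odds ratio = (s1/s0) / (r1/r0).

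Examples:

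| Retention | Odds ratio |
|---|---|
| THS arm 50% vs 65%, CC-use unselected | 0.50/0.65 = 0.77 |
| Same, CC-arm ratio r1/r0 = 0.85 | 0.77/0.85 = 0.90 (rounded down) |
| Same, CC-arm ratio 0.77 | 0.77/0.77 = 1.00 |
| THS-arm coughers stay more, 65% vs 50%, CC-use unselected | 0.65/0.50 = 1.30 |

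**3. V16, with only earlier cough affecting retention.** This simulation has no THS effect, cough prevalence 27.5%, a persistent subject effect (SD 1.8 on the logit scale), retention depending on any cough at V7 or V10, the CC arm unselected, and a logistic model adjusted for baseline cough:

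| Retention, coughers/non-coughers | V16 odds ratio |
|---|---|
| 55/63% | 0.96 |
| 50/65% | 0.93 |
| 45/68% | 0.89 |
| 40/72% | 0.84 |

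Analysed by randomised arm, the odds ratio is 0.99.

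**4. At trial size.** The sample-size section gives 475 × 0.65 = 309 per arm enrolled and 309 × 0.60 = 185 in THS-use. A second simulation used 309 per arm, 60% in THS-use and 30% prevalence, with 800 runs per setting. With persistent cough it gave:

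| Retention ratio | Mean odds ratio by use | 95% CI wholly below 1 (nominal 2.5%) |
|---|---|---|
| 0.8 | 0.93 | about 4–6% |
| 0.6 | 0.85–0.87 | about 9–10% |
| 0.4 | 0.72–0.79 | about 20–25% |

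By randomised arm the mean odds ratio was 0.98 to 1.02. If V16 cough is independent of earlier cough, the V16 bias disappears (about 1.0).

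**5. Against sampling error.** With 185 versus 309 subjects and 30% prevalence, SE(log odds ratio) = √[1/(185 × 0.21) + 1/(309 × 0.21)] = 0.20. A null interval runs from about 0.67 to 1.49. A shift to 0.93 (log −0.073) is about 0.4 SE.

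**The case against.** Three stronger readings are tempting, and the documents do not support them.

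- *There is no randomised information on cough.* Counts by randomisation arm are planned in SAP 12.7.2.5. FAS-EX is FAS-AR restricted to subjects with at least one diary record, so those counts are close to as-randomised, and a crude odds ratio follows from them. What is missing is an adjusted, modelled one. The listed title of Table 15.2.4.9.1 does not mention arm. The PP summary does not help, because PP is itself selected on use.
- *The odds ratio is biased in favour of THS.* The direction is possible, not established. It depends on who leaves in both arms.
- *SAP 16.2 denies that felt effects drive tobacco use.* It says only that the drivers differ from a pharmaceutical setting and that risk reduction may not be the main one. The sentence on detectable effects describes drug trials.

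Further points stand. Protocol 12.6.2 also specifies only use-based contrasts for cough, so the SAP follows it. FTND and ITUQ also have no FAS-AR analysis; MCEQ has none either, although its arms are compared. Objective 5 is descriptive, there are no formal hypotheses, and SAP section 9 removed p-values for cough. Moderate selection is small against the sampling error. These points limit the weight of the concern. They do not answer it: SAP section 10 names questionnaires among the FAS-EX outcomes and then commits in general to a FAS-AR sensitivity analysis, and the cough section has none.

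**Conclusion.** The point holds as a gap in supportive analysis. The cough model is run only on groups that use after a cough report helps to form, so its odds ratio can depart from 1 with no THS effect, and baseline adjustment does not remove this. No covariate-adjusted odds ratio with interval by randomised arm is planned, although the other markers under the same objective have by-arm models.

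The size is illustrative: about 0.84 to 0.96 at V16 if only THS-arm coughers leave at the assumed rates, given that cough persists within subjects. It moves towards or above 1 if CC-arm coughers leave CC-use too, or if coughing smokers stay on THS. For a descriptive secondary endpoint without p-values, this is a low-cost improvement and does not affect the primary analysis.

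**What to change.** In SAP 12.7.2.5, add the same GLIMMIX model on FAS-AR with randomisation arm in place of product use category, reported at V7, V10 and V16. Add one table beside 15.2.4.10, and state that the FAS-EX odds ratio is read together with it. SAP 12.7.1.3.2 already makes this substitution for the primary endpoints.

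The cost is one more run of existing code and one table; nothing planned is removed. The by-arm estimate has its own limits. It is diluted by non-adherence and is affected at V16 by non-enrolment in the extension, so V7 and V10 are its cleanest time points. It also does not remove open-label reporting bias.

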## **12.7.2.6 Subjective Effects of Smoking**

### **12.7.2.6.1 Modified Cigarette Evaluation Questionnaire**

The MCEQ assessment is described in Section 7.2.2 “Modified Cigarette Evaluation Questionnaire”.

Descriptive analysis for change from Baseline will be presented for the five domain scores at V7, V10, and V16. Scores and changes from Baseline will be listed and summarized (Listing 15.3.4.1; Tables 15.2.4.11.1 and 15.2.4.11.2). The answers to the individual questions will be included in the listings.

In addition, the MMRM analysis approach adopted in Section 12.7.1.2 “Smokers’ Health Profile Endpoints Evaluation” will be used for the five domain scores to evaluate the mean difference between THS-use and CC-use at V7, V10, and V16, using a 5% Type I error with no adjustment for multiplicity (Tables 15.2.4.12.1 and 15.2.4.12.2). The analysis will also be conducted on THS 2.2 vs CC arm. The models will only include terms for visit, sex, Caucasian origin, age, smoking intensity, baseline score, product use pattern category, and the interactions of visit with both baseline score and product use category. Site will be included as a random effect. The mean differences will also be described for Dual-use versus CC-use categories, using a 5% Type I error. The estimates of the difference will be presented together with 95% CI for THS 2.2 versus CC arms.

All summaries and analyses will be performed on FAS-EX and PP populations.

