7.7.2.3 Modified Cigarette Evaluation Questionnaire

Subjects will complete themselves the modified cigarette evaluation questionnaire (MCEQ) [38] according to Appendix 1 .

The MCEQ assesses the degree to which subjects experience the reinforcing effects of smoking, by measuring:

- Smoking satisfaction (satisfying, tastes good, and enjoys smoking).
- Psychological rewards (calms down, more awake, less irritable, helps concentrate, reduces hunger).
- Aversion (dizziness, nauseous).
- Enjoyment of respiratory tract sensations (single-item assessment).
- Craving reduction (single-item assessment).

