12.4 Analysis Population

The Full Analysis Set – as Exposed (FAS-EX) will be the primary analysis set for clinical risk endpoints, BoExp, and questionnaires, based on the overall product use pattern categories.

Confidentiality Statement

Data and information contained in this document are considered to constitute trade secrets and confidential commercial information, and the legal protections provided to such trade secrets and confidential information are hereby claimed under the provisions of applicable law. No part of this document may be publicly disclosed without the written consent of Philip Morris Products S.A.

Supportive analyses will be run on the per-protocol (PP) population and a sensitivity analysis will be conducted on the Full Analysis Set – as Randomized (FAS-AR).

The primary population for the assessment of safety will be the safety population. Safety will be summarized and presented by randomization arm and according to product use pattern categories.

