12.6.2 Descriptive Analysis

The number of CC or THS Tobacco Sticks used daily (as reported on the self-reported product use electronic diary) will be described over time on FAS-AR, FAS-EX, and on the safety population.

The levels of the BoExp and nicotine exposure level and their percent change from Baseline will be listed and summarized over the 12-month study period for the FAS-AR, FAS-EX and PP population.

The levels of lung function and CVD clinical risk endpoints will be summarized for the FAS-EX over the 12-month study period, along with change from baseline.

A supportive analysis will be conducted on the “smokers’ health profile” endpoints for the FAS-EX, FAS-AR, and PP population to compare the THS-use versus CC-use, and Dual-use versus CC-use at V16 by means of the MMRM approach used for the primary analysis. The estimates of the difference/percent reduction (and 2-sided p-values) will be presented together with 95% CI for THS-use versus CC-use and Dual-use vs CC-use. The same approach will be adopted for the analysis of BoExp, lung function, and CVD risk endpoints.

The number and percentage of subjects reporting a cough will be summarized for FAS-EX over the 12-month study period. A logistic regression model will be used to evaluate the differences between incidence rates (with 2-sided p-values) and 95% CI for the need to cough between THS-use and CC-use at V16. The models will only include terms for visit, baseline level and its interaction with visit, sex, Caucasian origin, and product use pattern category and its interaction with visit. The point and 95% CI of LS means of the incidence rates and their difference (with 2-sided p-values) will also be produced for Dual-use versus CC-use. The responses to the individual items, including the VAS score and change from Baseline, and 3 Likert scales measuring the intensity and frequency of cough, and the amount of sputum production will be listed and summarized for all subjects who filled in the questionnaire.

The change from Baseline will be calculated for the five domain scores of the MCEQ for the FAS-AR, FAS-EX and PP population over the 12-month study period. Scores and changes from baseline will be listed and summarized.

The FTND score and the number and percent of subjects in each category of the FTND score and of the response to the first item of the FTND will be summarized for FAS-EX and PP population

Confidentiality Statement

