## 9 CHANGES FROM THE PROTOCOL SPECIFIED STATISTICAL ANALYSIS

The following changes from the protocol specified statistical analysis were identified prior to database lock:

- Additional endpoints collected in the study but not listed in Section 3 of the protocol are reported in Section 5.3 “Additional Endpoints”. This includes residual volume which was not included in the protocol objectives but will be derived for interpretation of lung volume. Also, the Apo B/Apo A1 ratio will be analyzed and results will be used for the interpretation of Apolipoprotein data. The quantity excreted in 24h will be derived from the laboratory for Albumin as additional risk marker associated with CVD and renal disease. Spirometry (clinical interpretation and COPD categories), Respiratory symptoms (cough assessment VAS and Likert scales), and Body weight and BMI were not detailed as safety endpoints in Section 3 (Study Objectives) of the protocol but were considered for safety analysis in Section 12.6.4 of the protocol and are analyzed accordingly, in line with analyses from the original study.
- The definition of safety periods in Section 12.6.4 of the protocol showed that V3 is included in the Screening period and excluded from the Product trial period. However, in line with emergent events starting at enrollment, V3 is now excluded from the Screening period and included with the Product trial period instead.
- The distribution of product use cross-tabulation summary outlined in Section 12.7.2.1 will be summarized over the entire 12 month exposure period across the main and extension studies rather than the 6 months specified in the protocol.
- Clarified in Section 10.1 which visits are included in FAS-AR definition.
- The analysis of cough symptoms specified in Section 12.6.2 of the protocol was updated to present odds ratios rather than incidence rate differences because of use of the logistic model. The original model using the identity link to provide incidence rate differences could lead to convergence issues and so the approach was changed. In addition, age and smoking intensity were included in the logistic model, for consistency with the model used for other endpoints. Also, p-values will not be calculated.
- Inferential analyses in Sections 12.7.1, 12.7.2, and 12.7.3 will be presented at Months 3 and 6 in addition to Month 12.

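### The SAP drops the protocol's FAS-AR summaries of the MCEQ without listing the change, and does not say in which population its added THS 2.2 versus CC arm comparison is run

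*SAP*

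**What the plan says.** Protocol 12.6.2 covers the MCEQ in one short paragraph: "The change from Baseline will be calculated for the five domain scores of the MCEQ for the FAS-AR, FAS-EX and PP population", over the 12 months, and then "Scores and changes from baseline will be listed and summarized". It names no model and no between-group estimate for this questionnaire. Protocol 12.4 sets the hierarchy of populations: "The Full Analysis Set – as Exposed (FAS-EX) will be the primary analysis set for clinical risk endpoints, BoExp, and questionnaires".

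SAP 12.7.2.6.1 goes further on method and less far on populations. It adds the MMRM used for the primary endpoints, comparing THS-use with CC-use at V7, V10 and V16 "using a 5% Type I error with no adjustment for multiplicity". It also plans Dual-use against CC-use, and a comparison of the THS 2.2 and CC arms with 95% CIs. It closes with "All summaries and analyses will be performed on FAS-EX and PP populations". The list of tables in SAP 16.4 matches: two descriptive and two model tables for the MCEQ, one of each for FAS-EX and PP.

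**The concern.** The SAP removes a population that the protocol names, and the section meant to record such changes is silent. This matters more for the MCEQ than for most secondary endpoints because of what it measures: "The MCEQ assesses the degree to which subjects experience the reinforcing effects of smoking", with satisfaction, psychological reward, aversion and craving reduction among its subscales. These are plausible reasons for staying with a product or leaving it. Groups formed by use after randomization may therefore be selected on something close to the outcome.

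FAS-AR compares subjects by assigned arm and so does not use that grouping. Without it, a reader of the results for secondary objective 6 may have no comparison by randomized arm to set beside the comparisons by actual use. The SAP does not say whether its own arm comparison would fill that gap.

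**Working it through.** No figure in the plan is in dispute. The check compares the texts and adds one piece of arithmetic.

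1. **Sets named.** Protocol 12.6.2 has FAS-AR, FAS-EX and PP. SAP 12.7.2.6.1 has FAS-EX and PP. SAP 16.4 has Tables 15.2.4.11.1 and 15.2.4.11.2 (descriptive) and 15.2.4.12.1 and 15.2.4.12.2 (model), again FAS-EX and PP. The omission is consistent within the SAP, so it is not a slip in one sentence.

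2. **Disclosure.** SAP Section 9 opens with "The following changes from the protocol specified statistical analysis were identified prior to database lock" and goes down to details such as which safety period contains V3. It mentions neither the MCEQ populations nor the added MCEQ model.

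3. **Practice elsewhere.** The SAP's default for descriptive summaries (12.1.3) includes FAS-AR by arm. FAS-AR is kept for the smokers' health profile (12.7.1.3.2), biomarkers of exposure (12.7.2.2), nicotine exposure (12.7.2.3), and lung function and cardiovascular markers (12.7.2.4.1). In Protocol 12.6.2 the MCEQ is the only questionnaire for which FAS-AR is named: cough is on FAS-EX, and the FTND and ITUQ are on FAS-EX and PP.

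4. **Where the arm comparison would fall.** SAP 12.1.3 summarizes FAS-EX by use category, and FAS-AR and PP by arm. SAP 12.7.1.3.1, 12.7.1.3.2, 12.7.2.2 and 12.7.2.4.1 tie model-based arm contrasts to FAS-AR and PP. With FAS-AR removed, the same convention leaves PP. By SAP 10.3, everyone in PP randomized to THS 2.2 is THS-use and everyone randomized to CC is CC-use. Within PP, arm and use category therefore coincide, and an arm contrast there is still a contrast of use groups.

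5. **How much of the THS 2.2 arm the main contrast leaves out.** Inputs from SAP Section 8: 475 randomized per group, about 60% of the THS 2.2 arm expected in THS-use, and 20% lost to drop-out or insufficient diary data.
   - If the 60% applies to the whole arm: 475 × 0.60 = 285 in, and 475 − 285 = 190 out (40%).
   - If it applies after the 20% loss (an assumption): 475 × 0.80 × 0.60 = 228 in, and 475 − 228 = 247 out (247/475 = 52%).

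   Some of those left out appear in the Dual-use contrast. Others appear in none: under SAP Table 20, a subject who is THS-use in the first six months and CC-use in the second becomes a Switcher, which is pooled into Other-use and not compared. The CC-use definition in SAP Table 1 has no arm condition, so a THS 2.2-arm subject with almost no THS use can fall in the comparator group.

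These shares describe coverage. They are not estimates of bias.

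**The case against.** Four points can be made for the SAP.

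- **FAS-EX is not a set of persistent users.** SAP 10.2 defines it as all FAS-AR subjects with at least one diary record after randomization. An arm comparison run on FAS-EX would lose only subjects with no diary record, a number the documents do not give, and would be close to an as-randomized analysis. SAP 12.7.2.6.1 does not rule this out. This stands. It makes the defect an unstated population, not a proven restriction to PP.
- **What was removed is descriptive.** The protocol promised FAS-AR summaries, not an MCEQ effect estimate, and FAS-EX was already primary for questionnaires. This also stands. An FAS-AR model table goes beyond the protocol. The reason for asking for it is that the SAP itself added a model and an arm comparison.
- **The objective concerns switchers.** Secondary objective 6 compares smokers who switched with those who continued on CC, and SAP 16.2 explains why actual use is preferred. That supports keeping FAS-EX primary. It does not explain dropping FAS-AR for the MCEQ when the SAP keeps it for the other endpoints in step 3.
- **FAS-AR is not a clean measure of liking THS 2.2.** The items in SAP Table 6 ask about smoking and cigarettes, and neither document says which product a THS 2.2-arm subject is rating. Those who returned to CC may be rating CC. This stands and limits what can be said about direction.

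**Conclusion.** The conflict between protocol and SAP is real, undisclosed and confirmed by the table list. The population for the added arm comparison is not stated. Read with the SAP's own convention, MCEQ effects would be estimated only through groups defined by use after randomization, or in PP, where the THS 2.2 arm contains only THS-use subjects. That reading is the natural one, but it is an inference.

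Two stronger readings are tempting and are not supported. A reader might infer that MCEQ effects are estimated only in subjects who kept using THS 2.2. The definition of FAS-EX, the Dual-use contrast and the planned arm comparison all prevent that claim. A reader might also infer that the omission makes THS 2.2 look more satisfying relative to CC, and try to put a number on it. Any such number needs a correlation between liking and continued use, and a standard deviation for the scores, that the documents do not give. Its sign depends on which product subjects were rating. Selection related to the outcome is plausible; its direction and size cannot be set from the documents.

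The weight is moderate: one non-primary questionnaire in a study with no formal hypotheses, but an inexpensive correction that brings the SAP back to its protocol.

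**What to change.** - In SAP 12.7.2.6.1, restore FAS-AR beside FAS-EX and PP. Add to SAP 16.4 one descriptive table and one MMRM table by randomized arm at V7, V10 and V16, using the same model with randomization arm in place of product use category.
- State that the comparison of the THS 2.2 and CC arms is run on FAS-AR as well as PP.
- Keep FAS-EX as the primary set, and describe the THS-use and PP results as applying to subjects classified by actual use.
- List in Section 9 any departure that remains, including the MCEQ model that the protocol's MCEQ paragraph does not mention.

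The cost is two tables from existing data and code and a few lines of SAP text. No new data are needed, and the protocol already calls for the descriptive table.
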